## DEFINITION OF SAE

If an event is not an AE per definition above, then it cannot be an SAE even if serious conditions are met.

### Serious Adverse Events

Serious Adverse Event Definition: Any untoward medical occurrence that, at any dose:	
Results in death	Is life-threatening (defined as an event in which the subject was at risk of death at the time of the event; it does not refer to an event which hypothetically might have caused death if it were more severe)
Requires inpatient hospitalization or causes prolongation of existing hospitalization (see note below)	
Note: The following hospitalizations are not considered SAEs in BMS clinical studies:
 

• a visit to the emergency room or other hospital department <24 hours, that does not result in admission (unless considered an important medical or life-threatening event)

• elective surgery, planned prior to signing consent

• admissions as per protocol for a planned medical/surgical procedure

• routine health assessment requiring admission for baseline/trending of health status (eg, routine colonoscopy)

• medical/surgical admission other than to remedy ill health and planned prior to entry into the study. Appropriate documentation is required in these cases.

• admission encountered for another life circumstance that carries no bearing on health status and requires no medical/surgical intervention (eg, lack of housing, economic inadequacy, caregiver respite, family circumstances, administrative reason)

• admission for administration of anticancer therapy in the absence of any other SAEs (applies to oncology protocols)

Results in persistent or significant disability or permanent damage	
Is a congenital anomaly/birth defect	Is an important medical event (defined as a medical event(s) that may not be immediately life-threatening or result in death or hospitalization but, based upon appropriate medical and scientific judgment, may jeopardize the subject or may require intervention [eg, medical, surgical] to prevent one of the other serious outcomes listed in the definition above). Examples of such events include, but are not limited to, intensive treatment in an emergency room or at home for allergic bronchospasm; blood dyscrasias or convulsions that do not result in hospitalization. Potential drug-induced liver injury (DILI) is also considered an important medical event (see Section 8.2.8 for the definition of potential DILI).

Pregnancy and potential DILI must follow the same transmission timing and processes to BMS as used for SAEs (see Section 8.2.6 for reporting pregnancies).

## Evaluating AEs and SAEs

### Assessment of Intensity

The intensity of AEs is determined by a physician and will use the following levels:

- Mild: An event that is easily tolerated by the subject, causing minimal discomfort, and not interfering with everyday activities.
- Moderate: An event that causes sufficient discomfort and interferes with normal everyday activities.
- Severe: An event that prevents normal everyday activities. An AE that is assessed as severe should not be confused with an SAE. Severe is a category utilized for rating the intensity of an event; and both AEs and SAEs can be assessed as severe.

### Assessment of Causality

- The investigator is obligated to assess the relationship between study intervention and each occurrence of each AE/SAE. A “reasonable possibility of a relationship” conveys that there are facts, evidences, and/or arguments to suggest a causal relationship rather than a relationship cannot be ruled out.
- The investigator will use clinical judgment to determine the relationship.
- Alternative causes, such as underlying disease(s), concomitant therapy, and other risk factors, as well as the temporal relationship of the event to study intervention administration will be considered and investigated.
- The investigator will also consult the Investigator Brochure (IB) and/or Product Information, for marketed products, in his/her assessment.
- For each AE/SAE, the investigator must document in the medical notes that he/she has reviewed the AE/SAE and has provided an assessment of causality.
- There may be situations in which an SAE has occurred and the investigator has minimal information to include in the initial report to Sponsor. However, it is very important that the investigator always make an assessment of causality for every event before the initial transmission of the SAE data to Sponsor.
- The investigator may change his/her opinion of causality in light of follow-up information and send a SAE follow-up report with the updated causality assessment.
- The causality assessment is one of the criteria used when determining regulatory reporting requirements.

### Follow-up of AEs and SAEs

If only limited information is initially available, follow-up reports are required. Note: Follow-up SAE reports must include the same investigator term(s) initially reported.

If an ongoing SAE changes in its intensity or relationship to study drug or if new information becomes available, the SAE report must be updated and submitted within 24 hours to BMS (or designee) using the same procedure used for transmitting the initial SAE report.

All SAEs must be followed to resolution or stabilization.

## **Reporting of SAEs to Sponsor or Designee**

SAEs, whether related or not related to study drug, and pregnancies must be reported to [REDACTED] Drug Safety within 24 hours of awareness of the event.

SAEs must be recorded on the SAE Report Form. For studies capturing SAEs through electronic data capture, electronic submission is the required method for reporting. In the event the electronic system is unavailable for transmission, paper forms must be used and submitted immediately. When paper forms are used, the original paper forms are to remain on site.

Pregnancies must be recorded on a paper Pregnancy Surveillance Form and transmitted via email or confirmed facsimile (fax) transmission to:

**SAE Email Address:** [REDACTED]

## **APPENDIX 4      WOMEN OF CHILDBEARING POTENTIAL DEFINITIONS AND METHODS OF CONTRACEPTION**

### **DEFINITIONS**

#### **Woman of Childbearing Potential (WOCBP)**

A woman is considered fertile following menarche and until becoming postmenopausal unless permanently sterile. Permanent sterilization methods include hysterectomy, bilateral salpingectomy, and bilateral oophorectomy.

#### **Women in the following categories are not considered WOCBP**

- Premenarchal
- Premenopausal female with 1 of the following:
  - Documented hysterectomy
  - Documented bilateral salpingectomy
  - Documented bilateral oophorectomy

Note: Documentation can come from the site personnel's review of the subject's medical records, medical examination, or medical history interview.

- Postmenopausal female
  - A postmenopausal state is defined as 12 months of amenorrhea in a woman over age 45 years in the absence of other biological or physiological causes. In addition, females under the age of 55 years must have a serum follicle-stimulating hormone, (FSH) level  $>40$  mIU/mL to confirm menopause.

Note: Females treated with hormone replacement therapy, (HRT) are likely to have artificially suppressed FSH levels and may require a washout period in order to obtain a physiologic FSH level. The duration of the washout period is a function of the type of HRT used. The duration of the washout period below are suggested guidelines and the investigators should use their judgment in checking serum FSH levels.

- 1-week minimum for vaginal hormonal products (rings, creams, gels)
- 4-week minimum for transdermal products
- 8-week minimum for oral products

Other parenteral products may require washout periods as long as 6 months. If the serum FSH level is  $>40$  mIU/ml at any time during the washout period, the woman can be considered postmenopausal.

## CONTRACEPTION GUIDANCE FOR FEMALE SUBJECTS OF CHILD BEARING POTENTIAL

One of the highly effective methods of contraception listed below is required during study duration and until the end of relevant systemic exposure, defined as 3 days after the end of study treatment, plus 30 days.

Local laws and regulations may require use of alternative and/or additional contraception methods.

### Highly Effective Contraceptive Methods That Are User Dependent

*Failure rate of <1% per year when used consistently and correctly.a*

- Combined (estrogen- and progestogen-containing) hormonal contraception associated with inhibition of ovulationb
  - oral
  - intravaginal
  - transdermal
- Progestogen-only hormonal contraception associated with inhibition of ovulationb
  - oral
  - injectable

### Highly Effective Methods That Are User Independent

- Implantable progestogen-only hormonal contraception associated with inhibition of ovulationb
- Intrauterine device (IUD)c
- Intrauterine hormone-releasing system (IUS)c
- Bilateral tubal occlusion
- Vasectomized partner

*A vasectomized partner is a highly effective contraception method provided that the partner is the sole male sexual partner of the WOCBP and the absence of sperm has been confirmed. If not, an additional highly effective method of contraception should be used.*

- Sexual abstinence

*Sexual abstinence is considered a highly effective method only if defined as refraining from heterosexual intercourse during the entire period of risk associated with the study treatment. The reliability of sexual abstinence needs to be evaluated in relation to the duration of the study and the preferred and usual lifestyle of the subject.*

- It is not necessary to use any other method of contraception when complete abstinence is elected.
- WOCBP subjects who choose complete abstinence must continue to have pregnancy tests, as specified in Section 5.1
- Acceptable alternate methods of highly effective contraception must be discussed in the event that the WOCBP subjects chooses to forego complete abstinence

NOTES:

a Typical use failure rates may differ from those when used consistently and correctly. Use should be consistent with local regulations regarding the use of contraceptive methods for subjects participating in clinical studies.

b Hormonal contraception may be susceptible to interaction with the study treatment, which may reduce the efficacy of the contraceptive method. Hormonal contraception is permissible only when there is sufficient evidence that the IMP and other study medications will not alter hormonal exposures such that contraception would be ineffective or result in increased exposures that could be potentially hazardous. In this case, alternative methods of contraception should be utilized.

c Intrauterine devices and intrauterine hormone-releasing systems are acceptable methods of contraception in the absence of definitive drug interaction studies when hormone exposures from intrauterine devices do not alter contraception effectiveness

### **Less Than Highly Effective Contraceptive Methods That Are User Dependent**

*Failure rate of >1% per year when used consistently and correctly.*

- Male or female condom with or without spermicide. Male and female condoms cannot be used simultaneously
- Diaphragm with spermicide
- Cervical cap with spermicide
- Vaginal Sponge with spermicide
- Progestogen-only oral hormonal contraception, where inhibition of ovulation is not the primary mechanism of action

### **Unacceptable Methods of Contraception**

- Periodic abstinence (calendar, symptothermal, post-ovulation methods)
- Withdrawal (coitus interruptus).
- Spermicide only
- Lactation amenorrhea method (LAM)

## **CONTRACEPTION GUIDANCE FOR MALE SUBJECTS WITH PARTNER(S) OF CHILD BEARING POTENTIAL.**

Male subjects with female partners of childbearing potential are eligible to participate if they agree to the following during the treatment and until the end of relevant systemic exposure.

- Inform any and all partner(s) of their participation in a clinical drug study and the need to comply with contraception instructions as directed by the investigator.
- Male subjects are required to use a condom for study duration and until the end of relevant systemic exposure defined as 3 days after the end of treatment in the male subject.
- Female partners of males participating in the study to consider use of effective methods of contraception until the end of relevant systemic exposure, defined as 3 days after the end of treatment in the male subject.
- Male subjects with a pregnant or breastfeeding partner must agree to remain abstinent from penile vaginal intercourse or use a male condom during each episode of penile penetration during the treatment and until 3 days after the end of treatment.
- Refrain from donating sperm for the duration of the study treatment and for 3 days after the end of treatment.

## **COLLECTION OF PREGNANCY INFORMATION**

Guidance for collection of Pregnancy Information and outcome of pregnancy on the Pregnancy Surveillance Form is provided in Section [8.2.6](#) and [APPENDIX 3](#).

**APPENDIX 5      STATIC PHYSICIAN'S GLOBAL ASSESSMENT OF PSORIASIS  
(sPGA)**

The static PGA is used to determine the subject's psoriasis lesions overall at a given time point. Overall lesions will be graded for erythema, induration, and scaling based on the scales below. The average of the 3 scales, which is rounded to the nearest whole number, is the final sPGA score.

Characteristics	Score	Rating Score
Erythema (E) (averaged over the whole body)		0 = No evidence of erythema, but post inflammatory hyper/hypopigmentation changes may be present 1 = Faint erythema 2 = Light red coloration 3 = Moderate red coloration 4 = Bright red coloration
Induration (I) (averaged over the whole body)		0 = No evidence of plaque elevation 1 = Minimal plaque elevation, barely palpable, = 0.25 mm 2 = Mild plaque elevation, slight but definite elevation, indistinct edge, = 0.5 mm 3 = Moderate plaque elevation, elevated with distinct edges, = 0.75 mm 4 = Severe plaque elevation, hard/sharp borders, $\geq 1$ mm
Scaling (S) (averaged over the whole body)		0 = No evidence of scaling 1 = Minimal; occasional fine scaling 2 = Mild; fine scale dominates 3 = Moderate; coarse scale predominates 4 = Severe; thick scale predominates

$$E + I + S = / 3 = (\text{Total Average})$$

Physician's Static Global Assessment based upon above Total Average

- 0 = Clear, except for residual discoloration
- 1 = Almost clear -majority of lesions have individual scores for  $E + I + S / 3$  that averages 1
- 2 = Mild -majority of lesions have individual scores for  $E + I + S / 3$  that averages 2
- 3 = Moderate -majority of lesions have individual scores for  $E + I + S / 3$  that averages 3
- 4 = Severe -majority of lesions have individual scores for  $E + I + S / 3$  that averages 4

Note: Scores should be rounded to the nearest whole number. If total  $\leq 1.49$ , score = 1; if total  $\geq 1.50$ , score = 2.

## APPENDIX 6 PSORIASIS AREA AND SEVERITY INDEX (PASI)

[figure not shown]
Psoriasis Area and Severity Index (PASI); a quantitative rating scale for measuring the severity of psoriatic lesions based on area coverage and plaque appearance. Please complete **all** sections of the table.

Plaque Characteristic	Rating score	Body region (and weighting factor)			
		Head	Upper Extremities	Trunk	Lower Extremities
Erythema (Redness)	0 = None 1 = Slight 2 = Moderate 3 = Severe 4 = Very severe				
Infiltration (Thickness)					
Desquamation (Scaling)					
Add together each of the 3 scores for each of the body regions to give 4 separate sub totals.					
Sub Totals		A1 =	A2 =	A3 =	A4 =
Multiply each subtotal by amount of body surface area represented by that region i.e. A1 x 0.1 for head, A2 x 0.2 for upper extremities, A3 x 0.3 for trunk, A4 x 0.4 for lower extremities to give a value B1, B2, B3 and B4 for each body region respectively					
		A1 x 0.1 = B1 B1 =	A2 x 0.2 = B2 B2 =	A3 x 0.3 = B3 B3 =	A4 x 0.4 = B4 B4 =
Degree of involvement as % for each body region affected; (score each region with score between 0-6)	0 = None 1 = 1-9 % 2 = 10-29% 3 = 30-49% 4 = 50 -69% 5 = 70-89% 6 = 90-100%				
For each body region multiply sub total B1, B2, B3 and B4 by the score (0-6) of the % of body region involved to give 4 subtotals C1, C2, C3 and C4					
		B1 x score = C1 C1 =	B2 x score = C2 C2 =	B3 x score = C3 C3 =	B4 x score = C4 C4 =
The patient's PASI score is the sum of C1 + C2 + C3 + C4				PASI=	

**APPENDIX 7 SCALP SPECIFIC PHYSICIAN'S GLOBAL ASSESSMENT  
(ss-PGA)**

Please rate overall scalp psoriasis severity by selecting the overall score based on the following rating scale:

[figure not shown]
Score	Category	Description
0	Absence of Disease	No evidence of redness, no evidence of thickness, and no evidence of scaliness on the scalp
1	Very Mild Disease	The overall clinical picture consists of flat lesions with barely perceptible erythema, with or without a trace of overlying fine scale
2	Mild Disease	The overall clinical picture consists of lesions with mild erythema, slight, but definite, thickness, and a thin scale layer
3	Moderate Disease	The overall clinical picture consists of lesions with moderate erythema, a moderate thickness, and a moderate scaled layer
4	Severe Disease	The overall clinical picture consists of lesions with bright erythema, severe thickness, and a severe, coarse thick scale layer

[figure not shown]

**APPENDIX 9 PHYSICIAN'S GLOBAL ASSESSMENT-FINGERNAILS (PGA-F)**

For this assessment in subjects with psoriasis fingernail involvement, the overall condition of the fingernails is rated by the investigator on a 0-4 (5-point) scale. The overall score assigned based on the higher of the nail bed/nail matrix score:

		Nail Bed Signs	Nail Matrix Signs
Clear	0	Onycholysis- consistent with a normal nail AND Hyperkeratosis- none AND Splinter Hemorrhages- consistent with non-psoriatic splinter hemorrhages AND Nail Bed Erythema- none	No non-psoriatic nail plate irregularities including pitting, crumbling, Beau's lines, senile onychorrhexis, and non-psoriatic leukonychia
Minimal	1	Onycholysis- < 10% involved on all nails OR Hyperkeratosis- present, but barely detectable elevation of nail plate OR Nail Bed Erythema- faint AND Splinter Hemorrhages- consistent with non-psoriatic splinter hemorrhages	No more than 5 pits or psoriatic leukonychia on any nail AND No crumbling
Mild	2	Onycholysis- > 10% on five or more nails OR Hyperkeratosis- present with mild elevation of nail plate OR Splinter Hemorrhages- present on four or fewer nails OR Nail Bed Erythema- mild	Five or more nails with mild pitting (eg, > 10 pits/nail) or psoriatic leukonychia AND No crumbling
Moderate	3	Onycholysis- > 30% on at least one nail OR Hyperkeratosis- present with moderate elevation of nail plate OR Splinter Hemorrhages- scattered and present on five or more nails OR Nail Bed Erythema- moderate	Five or more nails with moderate pitting (eg, > 25 pits/nail) AND ≤ 25% crumbling on any nails
Severe	4	Onycholysis- > 50% on at least one nail OR Hyperkeratosis- present with severe elevation of nail plate OR Splinter Hemorrhages- numerous and present on five or more nails OR Nail Bed Erythema- severe	Five or more nails with severe pitting (> 50 pits/nail) OR > 25% crumbling on any nail

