### 4.1.2 Secondary Endpoint(s)

#### 4.1.2.1 Key Secondary Endpoints for Comparisons to Placebo

The key secondary efficacy endpoints for BMS-986165 compared to placebo at Week 16 are defined as:

- PASI 90 response assessed as a proportion of subjects who achieve a 90% improvement from baseline in PASI score
- sPGA 0 response assessed as a proportion of subjects with an sPGA score of 0
- Scalp specific Physician's Global Assessment (ss-PGA) 0/1 assessed as a proportion of subjects with a ss-PGA score of 0 or 1 with at least a 2-point improvement from baseline among subjects with a baseline ss-PGA score  $\geq 3$
- PSSD symptom score of 0 assessed as a proportion of subjects with a PSSD symptom score of 0 among subjects with a baseline PSSD symptom score  $\geq 1$
- PASI 100 response assessed as a proportion of subjects who achieve a 100% improvement from baseline in PASI score
- Physician Global Assessment-Fingernails (PGA-F) 0/1 assessed as a proportion of subjects with a PGA-F score of 0 or 1 with at least a 2-point improvement from baseline among subjects with a baseline PGA-F score  $\geq 3$
- DLQI 0/1 assessed as a proportion of subjects with a DLQI score of 0 or 1 among subjects with a baseline DLQI score  $\geq 2$  (Ex-US submission only)

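### The Clear nail-matrix descriptor of the PGA-F is worded the wrong way round; read literally, it can change PGA-F 0/1 responder status in two narrow cases

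*Protocol*

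**What the plan says.** Protocol Appendix 9 scores the fingernails from 0 to 4 in two columns, nail bed and nail matrix. The overall score is the higher of the two.

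- **Clear (0), nail matrix:** "No non-psoriatic nail plate irregularities including pitting, crumbling", followed by Beau's lines, senile ridging (onychorrhexis) and leukonychia of non-psoriatic origin.
- **Clear (0), nail bed:** one of its conditions is "Splinter Hemorrhages- consistent with non-psoriatic splinter hemorrhages", so a non-psoriatic finding is acceptable at Clear.
- **Minimal (1), nail matrix:** "No more than 5 pits or psoriatic leukonychia on any nail", together with no crumbling.
- **Mild (2), nail matrix:** "Five or more nails with mild pitting (eg, > 10 pits/nail) or psoriatic leukonychia", together with no crumbling.
- **Moderate (3), nail matrix:** "Five or more nails with moderate pitting (eg, > 25 pits/nail"), together with crumbling of at most 25%.
- **Severe (4), nail matrix:** severe pitting (more than 50 pits per nail) on five or more nails, or crumbling above 25% on any nail.

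Protocol Section 8.1.1.6 and SAP Section 8.2.1.6 name the five grades without defining them, so neither corrects the Clear cell.

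The endpoint in SAP Section 4.1.2.1 is "Physician Global Assessment-Fingernails (PGA-F) 0/1 assessed as a proportion of subjects with a PGA-F score of 0 or 1", with at least a 2-point improvement, among subjects with a baseline score of 3 or more. Protocol Section 9.3.2.1 has the same endpoint without the improvement clause. SAP Section 6.1 tests key secondary endpoints at two-sided 0.025.

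**The concern.** A score of 0 should mean that no nail psoriasis is left. Appendices 7 and 11 define 0 that way for the scalp and palmoplantar scales. In Appendix 9 the adjective in the Clear matrix cell points the other way. Senile ridging or Beau's lines bar a score of 0, while psoriatic pitting, crumbling and leukonychia are not mentioned as barring it.

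This is a scoring rule for a key secondary endpoint. A rater who follows the text and one who infers the intent can score the same hand differently. SAP Section 8.2.1.6 describes collecting a single PGA-F rating, so on the data it describes, a score given under the wrong rule could not be re-derived later. What matters is whether the fault reaches the responder classification, which depends on the boundary between 1 and 2, not on the boundary between 0 and 1.

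**Working it through.** The documents give no sample size, response rate or power for PGA-F, so there is no planned figure to reproduce. The check is logical.

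**Step 1. Does confusing 0 with 1 change a responder?** Two baseline scores (3, 4) by five Week 16 scores (0 to 4) give 2 × 5 = 10 pairs. Responders are the four pairs with a Week 16 score of 0 or 1. The smallest improvement among them is 3 − 1 = 2, so the Protocol and SAP definitions agree. Exchanging 0 and 1 changes 0 of the 10 classifications.

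**Step 2. Which nail states cross the 1/2 boundary?** Apply the matrix column to illustrative states, with the nail bed at 0 or 1. Corrected means that Clear requires no psoriatic nail-plate signs and allows non-psoriatic ones.

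| State at Week 16 | Clear as printed | Minimal | Levels 2–4 | Score as printed | With Clear corrected |
|---|---|---|---|---|---|
| No psoriatic sign; Beau's lines or ridging | fails | meets | none | 1, responder | 0 or 1, responder |
| No psoriatic sign; 8 non-psoriatic pits on a nail | fails | fails | none | no level; neither 0 nor 1 available | 0, responder |
| No psoriatic sign; non-psoriatic crumbling of 30% | fails | fails | Severe | 4, nonresponder | Clear, but still matches Severe unless crumbling is limited to psoriatic |
| 15 psoriatic pits on each of five nails | meets | fails | Mild | 2 by worst matching level | 2 |
| 15 psoriatic pits on each of four nails | meets | fails | none | only Clear: 0, responder | no level |
| 10% psoriatic crumbling, no pitting | meets | fails | none | only Clear: 0, responder | no level |

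Rows 2 and 3 are the first route (false nonresponder). Rows 5 and 6 are the second (false responder). Rows 1 and 4 keep their responder status.

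**Step 3. A wider grid for the second route.** Take 0, 3, 8, 15, 30 or 60 psoriatic pits per nail on 0, 1, 4, 5 or 10 nails (zero pits only with zero nails), crumbling of 0, 10 or 30%, and psoriatic leukonychia on 0 or 5 nails. That is (1 + 5 × 4) × 3 × 2 = 126 states, with no non-psoriatic irregularity present.

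- All 126 satisfy the printed Clear text.
- 77 also meet at least one of levels 2 to 4 and keep that score if the worst matching level is used.
- 5 meet Clear and Minimal only, and are responders either way.
- 44 match Clear alone: 4 with 8 pits per nail, 6 with more than 10 pits on fewer than five nails, and 34 with 10% crumbling but without moderate pitting on five nails (4 + 6 + 34 = 44; 77 + 5 + 44 = 126).

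With Clear corrected, those 44 match no level. The reversed word therefore makes Clear their only literal home, and correcting it exposes gaps in the scale that also need closing. The grid points are arbitrary, so 44 of 126 says nothing about frequency in the trial. The pit thresholds for Mild and Moderate are given as examples, so the 6-to-10-pit gap is softer than the gap made by the five-nail count.

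**The case against.** The strongest reply is that the intent is obvious. The row is labelled Clear, the cell itself names pitting and crumbling as absent, and the higher of bed and matrix decides the score. Section 8.1.1.6 asks for a dermatologist or a trained investigator experienced in psoriasis, and Section 8 limits trained assessments to certified raters. Raters may never have applied the literal text, and the eCOA form and source instrument are not among the documents. This stands in part: it makes misclassification less likely, and it means the documents cannot show that the printed wording was used. It does not make the wording right.

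A second reply is that the gaps between levels, and the unqualified words pits and crumbling, are separate faults. That is correct, and the remedy has to cover them too.

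A reader might infer more than the text supports:

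- **That cleared nails with Beau's lines or age ridging become nonresponders.** They do not; they meet Minimal.
- **That active nails meeting levels 2 to 4 would be scored 0.** Each has its own descriptor, and under the worst matching level it keeps that score. Appendix 9 states a worst-score rule between columns only, so applying it within the matrix column is an assumption, though a natural one.
- **That a loss of power can be computed.** Subset size, response rates and misclassification rates would all be invented, and symmetric error across the responder boundary is not how this cell acts.
- **That failure here would make a series of later tests descriptive.** The test order in SAP Section 6.1.3 is not visible. In the visible text, Section 4.1.2.1 lists only DLQI 0/1 (ex-US submission) after PGA-F, and neither that list nor Appendix 1 is presented as the test order.

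**Conclusion.** The Clear matrix cell is wrong as written and contradicts the rest of its own table. For PGA-F 0/1 the consequence is limited to two cases under a literal reading:

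1. A psoriasis-free nail with non-psoriatic crumbling or more than 5 non-psoriatic pits fails both Clear and Minimal, and so cannot count as a response.
2. Active nails that fit none of levels 1 to 4 match only the printed Clear, and can count as a response if the nail-bed score is 0 or 1.

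The errors run in opposite directions, and their frequency cannot be estimated from the documents. Raters are blinded and use one scale in all arms, so the effect should be mainly non-differential. The conclusion assumes that raters saw the Appendix 9 wording and took it literally, which the documents neither confirm nor exclude. An analysis of score 0 alone would be affected directly, but no such PGA-F endpoint appears in the visible text.

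**What to change.** 1. **Correct the Clear matrix cell** so that it requires the absence of psoriatic nail-plate signs (pitting, crumbling, leukonychia) and states that non-psoriatic irregularities may be present.
2. **Add one sentence** that pits and crumbling in levels 1 to 4 mean psoriatic pits and crumbling.
3. **Assign a level to the states that fit none**, in particular more than 10 pits on fewer than five nails, 6 to 10 pits per nail, and crumbling of 25% or less without moderate pitting on five nails. Take the rule from the source instrument if it has one.
4. **Compare Appendix 9 with the eCOA form, the rater training and the source instrument**, and record any difference. SAP Section 6.6.1 says that all subjects remaining in the trial had completed Weeks 16 and 24 before the COVID-19 restrictions, so new wording cannot alter those ratings. If raters used the printed text, report it as a limitation of PGA-F 0/1. If they used a correct form, say so and treat Appendix 9 as a transcription error.

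The cost is one table cell, a clarifying sentence, the added level rules and a document comparison. It needs no subjects, visits or change to the analysis method.
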